### **PROCEDURES FOR MAINTAINING CONFIDENTIALITY**

Privacy: The recruitment and consent process will take place in the participants' home, in a private, quiet area. At those times they may ask any questions that they may have about the study. Participants are given the opportunity to conduct their questionnaire and provide the colonization swabs in any location in their own home. Some children like to stay by their parents to feel safer during the swabs. Others don't want to be seen when it is occurring and ask to go into a different room. We let them and their guardians decide how they want to proceed. The intervention (bleach baths, mupirocin) will take place when we are not in the home, and will be at their own discretion as to how they complete it as a family. All information we collect is relevant to learning about the transmission of *S. aureus* in the household environment so that we can learn how to prevent *S. aureus* infections. All participants are informed during the consent process that they can choose to not answer any question they feel uncomfortable answering

De-identification of data: Patient data and specimens will be coded with a study number to link the data with the specimens.

Data Security: Hard copy records will be transferred from homes to Washington University in a locked brief case. The records will be stored in a locked filing cabinet in a locked office. Participant data will be collected, entered, and stored electronically. All data will be protected with a secure computer network and password access. Specifically, The Division of Biostatistics Informatics Core will be used as a central location for data processing and

management. Washington University belongs to a consortium of institutional partners that work to maintain a software toolset and workflow methodology for electronic collection and management of research and clinical trial data. REDCap (Research Electronic Data Capture) data collection projects rely on a thorough study-specific data dictionary defined in an iterative self-documenting process by all members of the research team with planning assistance from the Division of Biostatistics Informatics Core. The iterative development and testing process results in a well-planned data collection strategy for individual studies. REDCap servers are securely housed in an on-site limited access data center managed by the Division of Biostatistics at Washington University. All web-based information transmission is encrypted. REDCap was developed specifically around HIPAA-Security guidelines and is implemented and maintained according to Washington University guidelines. The device we will use to enter data over the secure server is the IPAD 2. The IPAD will be password protected and only study team members will have access. All data will also be entered to the secure REDCap server and not stored anywhere else on the IPAD.

## **ASSESSMENT OF RISKS AND BENEFITS**

### Risks:

Likely / Common:

None

Less Likely / Less Common:

Mild

- Some questions the researchers will ask might make participants feel uncomfortable.
- Obtaining swabs from the nostrils, underarms, and groin area might be uncomfortable for some people.
- Dry skin may result from the use of dilute bleach water baths.

Rare:

Mild

- The mupirocin ointment applied to the nose may cause irritation such as itching, burning, or stinging.
- Bleach baths may cause a mild rash.
- All of these problems will go away once the participant stops using the products.
- There is a chance that the confidentiality of your participation could be breached.

Protection against potential risks: Participants will have the right to refuse to answer any question for any reason throughout the study. The risk of discomfort from the nasal swabs will be minimized by moistening the swab prior to culturing and by sampling the anterior portion of the nares. Decolonization products will be applied topically which poses minimum risk.

Participants will be instructed (orally and in writing) to contact the study team as well as their primary care providers or seek care from a local ED if they suspect they are experiencing adverse effects from their treatments. The primary care provider may prescribe an alternative treatment at any time during the study. In addition, participants will be closely followed by study personnel for the development of SSTI. Participant data will be protected with a secure computer network and password access. All hard-copy data will be protected in a locked office and locked file cabinet.

Benefits: Study participants may benefit from a decreased incidence of CA-MRSA disease, thereby eliminating the need for painful drainage procedures, potential hospitalization, and antibiotic administration. Even household members randomized to the "Individualized Decolonization Approach" group who are not assigned decolonization measures (because they

had not experienced SSTI during the 12-month natural history study) may benefit from the decolonization of household contacts as the burden of CA-MRSA in the household may decrease and subsequently reduce the risk of transmission. Participants will also receive education about the *Staph* germ. This project may decrease the incidence of CA-MRSA infections, and thus reduce healthcare utilization for CA-MRSA treatment, potentially preventing additional spread of virulent CA-MRSA strains. The project findings may lead to therapeutic and/or preventive advances that will benefit a large number of patients and have a positive impact on healthcare utilization and expenditures.

## **Statistical Plan**

Sample Size and Determination of Power: The expected rate of SSTI in individuals in the Household Approach group is 9% at 3 months based on one of our prior studies. An absolute difference of 10% is considered to be clinically equivalent and has been recommended for anti-infective trials; thus, 9% SSTI incidence in the Household Approach group and 19% SSTI incidence in the Individualized Approach group 3 months post-decolonization would be considered clinically equivalent. Considering the variance inflation factor due to clustering of participants within households (estimated to be 1.4 based on our prior studies), and considering 4 interim analysis for the primary outcome to be conducted under the Data Safety Monitoring Plan, a total sample of 344 participants (172 per group) or 86 total households (43 households per group) will have 80% power at alpha=0.05 to conclude that the SSTI incidence in the Individualized Decolonization Approach is not inferior to that of the Household Decolonization Approach with a non-inferiority margin of 10%. Sample size calculations were performed using PASS 11. "The Community-Associated Methicillin-Resistant Staphylococcus aureus (CA-MRSA) Among Household Members and the Home Environment" study (HRPO 201104330) will enroll 150 households (approximately 600 participants). Taking into consideration exclusion criteria, lost to follow-up and declining participation, we believe 25-35% of households will not enroll in the HOME 2 Decolonization Study, resulting in approximately 100 households enrolling in the trial. Anticipating 10% attrition from trial enrollment to the 3-month follow-up visit, we will have 90 households for analysis of the primary outcome SSTI at 3 months.

Analysis Plan: Descriptive statistics will be used to characterize the study population, the proportion of participants colonized and infected with MRSA over the course of the study, and the types and relatedness of colonizing and infecting strains recovered from participants.

The primary outcome, occurrence of SSTI 3 months after randomization, for all participants will be determined for the two groups: 1) Individualized Decolonization Approach and 2) Household Decolonization Approach. Three months was chosen as the time point for the primary outcome as this is a reasonable amount of time for individuals undergoing decolonization to reacquire the organism from other colonized household contacts and for a subsequent infection to develop. To test non-inferiority of the Individualized Approach versus the Household Approach, the difference in proportion of SSTI at 3 months and the 2-sided 95% confidence interval for the difference in proportions will be calculated. Non-inferiority will be defined as the upper limit of the 2-sided 95% confidence interval being less than 10% (our margin of non-inferiority). A 10% absolute difference is considered to be clinically equivalent and has been recommended for anti-infective trials. One thousand sample bootstrapping (household sampling with replacement) will be used to estimate the 95% confidence interval and account for clustering within households. The analysis will be performed on both the intention-to-treat population and the per-protocol population because the intention-to-treat analysis can be biased in non-inferiority trials. Secondarily, we will perform comparisons of SSTI recurrence among only participants who had an SSTI in the prior year.

We will also use longitudinal mixed effects logistic regression models using SAS PROC GLIMMIX to assess differences in colonization status, SSTI incidence, and confirmed MRSA infection over the entire course of the study (12 months) between the Household Approach group and the Individualized Approach group, adjusting for pertinent covariates accounting for clustering of individuals within households. Adherence to recommended hygiene practices and decolonization measures (application of mupirocin ointment twice daily for 5 days and daily bathing in dilute bleach water for 5 days) will be described and compared between the two groups using generalized linear mixed effects models, with appropriate link functions (e.g., log for number of days of bleach water baths or number of applications of mupirocin ointment). Adherence to decolonization measures will be compared only among individuals intended to receive the decolonization regimen (i.e., household members in the Individualized Approach group not assigned decolonization measures will not be included in the analysis). In addition, we will assess the level of adherence to each part of the intervention (hygiene practices, application of mupirocin ointment, bleach water baths) as risk factors for colonization and SSTI. All critical results will be validated with comparable generalized estimating equation (GEE) models. Reported adverse reactions will also be characterized and compared between the two treatment groups.

To test the relationship between environmental contamination at baseline and household characteristics with persistent colonization, we will use mixed effects logistic regression models with a random effect for household. Hypothesized risk factors include household surface contamination at baseline and household crowding. To test the relationship between environmental contamination at baseline with infection at follow-up time points, we will use longitudinal mixed effects logistic regression models. We will also incorporate CA-MRSA recovery from household environmental surfaces as a predictor of acquisition, infection, and colonization with the same strain.

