#### Data to be reviewed:

1. Adverse Events
  - a. Description of individual serious and non-serious adverse events
  - b. Rates of serious and non-serious adverse events by study group, and overall
2. Patient Recruitment and Retention
  - a. Eligibility and refusal rates for subjects
  - b. Reasons for exclusion

- c. Baseline demographic characteristics of randomized participants and household characteristics to check adequacy of randomization (including gender, race/ethnicity, number of household members overall, and number of individuals per household experiencing SSTI during the natural history study)
- d. Attrition rates by study group (only available during the follow-up period)

3. Outcomes
  - a. Incidence of SSTI (Primary outcome is SSTI incidence 3 months following decolonization)
  - b. MRSA colonization status of study participants
4. Protocol Violations
  - a. Descriptions of any protocol violations that occur

Stopping Criteria: Interim analysis for the primary outcome, incidence of SSTI 3 months following decolonization, will be conducted approximately every 6 months throughout the trial (~4 times). The trial will be terminated or modified upon interim data analysis if there is overwhelming evidence of the benefit of one treatment arm compared to the other arm of the study, defined as an absolute difference of 50% in the 3-month incidence of SSTI during the longitudinal study period between the Individualized Approach and Household Approach arms. The Lan-DeMets spending function approach will be used to examine our primary outcome when interim analyses are performed to allow for flexible interim monitoring while also preserving the type-I error of the study.

Reporting: A safety and interim analysis report will be generated by the monitors twice annually. As required by the WU HRPO, the PI will report the following serious adverse events to the WU HRPO using methods specified by the WU HRPO: deaths will be reported immediately, life-threatening events will be reported within 7 calendar days, and all other serious adverse events will be reported within 15 calendar days.

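### The final non-inferiority test uses a full two-sided 95% interval, which does not fit a plan that also spends alpha on, and sizes for, about four interim looks at the same outcome

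*Combined protocol and SAP*

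**What the plan says.** Three places bear on the level of the primary test.

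- **Statistical Plan, Analysis Plan.** The final rule is: "Non-inferiority will be defined as the upper limit of the 2-sided 95% confidence interval being less than 10% (our margin of non-inferiority". The interval comes from a household bootstrap: "One thousand sample bootstrapping (household sampling with replacement) will be used to estimate the 95% confidence interval". Neither sentence refers to interim looks.
- **Statistical Plan, Sample Size and Determination of Power.** The calculation was made "considering 4 interim analysis for the primary outcome to be conducted under the Data Safety Monitoring Plan", and concludes that "a total sample of 344 participants (172 per group) or 86 total households (43 households per group) will have 80% power at alpha=0.05" for non-inferiority with a 10-point margin. Whether alpha is one-sided or two-sided is not stated.
- **Data and Safety Monitoring Plan, Stopping Criteria.** Interim analyses of the primary outcome "will be conducted approximately every 6 months throughout the trial (~4 times"). "The Lan-DeMets spending function approach will be used to examine our primary outcome when interim analyses are performed", with the aim "to allow for flexible interim monitoring while also preserving the type-I error of the study". The only numerical stopping threshold is overwhelming benefit of one arm, "defined as an absolute difference of 50% in the 3-month incidence of SSTI".

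The plan does not give the spending function, the information fractions, the overall one-sided level or the level left for the final analysis.

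**The concern.** A spending function controls the type I error only if the final analysis uses what the earlier looks have left. Here the final analysis gets the whole 0.025, as if the data were examined once, while the sample size treats non-inferiority as a test with interim looks. If the looks do spend alpha on non-inferiority, the final level should follow from the spending function, and 95% does not. If they do not, the sample size had no reason to count them. On either reading one of the passages has to change.

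The comparison of the upper limit with 10 points is the whole primary verdict, so a borderline result could pass at one level and fail at another. The investigator and the trial biostatistician are among the monitors who review interim data, so a level settled later would be open to challenge.

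**Working it through.** **Inputs from the documents.** 9% SSTI at 3 months, taken as equal in both arms for power; margin 10 points; variance inflation 1.4; 172 per group; 80% power; alpha 0.05; about four interim looks.

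**Assumptions.** Equally spaced looks. Four analyses in all, or four interims plus a final (five), since the text allows either. O'Brien-Fleming-type and Pocock-type spending as two common choices. Normal approximation.

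**1. The stated 172 per group.** Fixed design: n = 2 × 0.09 × 0.91 × (z_alpha + 0.842)² / 0.10² × 1.4.
- One-sided 0.025: 128.6 × 1.4 = 180.0, already above 172 before any looks.
- One-sided 0.05: 101.3 × 1.4 = 141.8 with no looks.
- One-sided 0.05 with Pocock-type spending: 141.8 × 1.204 = 170.7 (four analyses) or 141.8 × 1.2215 = 173.2 (five).

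The last line brackets 172, which suggests an overall one-sided 0.05. The match is not unique: a continuity-corrected one-sided 0.05 calculation with no looks gives about 169.

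**2. Standard error and passing threshold.** SE = √(2 × 0.09 × 0.91 × 1.4 / 172) = 0.0365. At 95% the largest observed difference that passes is 10 − 1.96 × 3.65 = 2.84 points.

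**3. If non-inferiority is tested at every look.** Lan-DeMets boundaries were found by recursive numerical integration. The overall error was then recomputed with the final multiplier set to 1.96. Ranges run over four and five analyses.

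| One-sided total | Spending type | Final multiplier | Matching two-sided interval | Overall error with final 1.96 | Largest passing difference at the matching level |
|---|---|---|---|---|---|
| 0.025 | O'Brien-Fleming | 2.01–2.03 | 95.6–95.8% | 0.028 | 2.6–2.7 points |
| 0.025 | Pocock | 2.35–2.39 | 98.1–98.3% | 0.037 | 1.3–1.4 points |
| 0.05 | O'Brien-Fleming | 1.72–1.74 | 91.5–91.8% | 0.036–0.038 | 3.7 points |
| 0.05 | Pocock | 2.04–2.07 | 95.8–96.2% | 0.053–0.054 | 2.4–2.6 points |

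Against 2.84 points, the band in which the verdict changes is about 0.2 to 1.6 points wide. With five analyses, a 0.025 total and equal true rates, about 2% (O'Brien-Fleming-type) or 14% (Pocock-type) of trials would fall in it.

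**4. If the 50-point difference is the only way to stop.** At the non-inferiority null (19% against 9%) and the first of five analyses (172 / 5 = 34.4 per arm), SE = √(1.4 × (0.0819 + 0.1539) / 34.4) = 0.098. A false non-inferiority claim would need the Individualized arm to be 50 points better, which is (0.50 + 0.10) / 0.098 = 6.1 standard errors from the null. The looks then use essentially no alpha, and a final 1.96 keeps 0.025.

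**5. Power at 172 per group.** Unadjusted 95% rule: 0.10 / 0.0365 − 1.96 = 0.78, or 78.2%. With a one-sided 0.025 total spent over the looks: about 77% (O'Brien-Fleming-type) or 69–70% (Pocock-type).

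**The case against.** The strongest reply is that no passage allows non-inferiority to be declared early. The only numerical rule stops the trial for a 50-point benefit of one arm, and step 4 shows that this leaves the final test intact. That stands, and it is the reading closest to the stopping text. It does not settle the matter: on that reading the sample size should not count the looks for this test, and the plan still does not say what its Lan-DeMets boundary is for.

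A reader might infer that the final interval must be wider than 95%. The documents do not support that. Alpha in the sample size paragraph has no stated sidedness, and with a one-sided 0.05 total and O'Brien-Fleming-type spending an interval of about 91.5–91.8% would suffice, so 95% would be stricter than needed.

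A reader might also infer that the plan states two conflicting levels, or that the true error is twice what the final rule implies. Only one final level is given as a number; the other has to be derived from choices that the plan leaves open. The figure near 0.053 belongs to designs with a 0.05 total, so the excess over their own target is only about 0.003.

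Finally, with O'Brien-Fleming-type spending at 0.025 the effect is small. The disputed band is about 0.2 to 0.3 points, while the Monte Carlo error of a percentile limit from 1,000 bootstrap samples is about √(0.975 × 0.025 / 1000) / 0.0584 × 3.65 = 0.31 points. This also stands, and it limits the weight of the point.

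**Conclusion.** The point holds as an inconsistency in the decision level, not as proof of material error inflation. The unadjusted 95% rule does not fit a sample size that counts the looks and a monitoring plan that spends alpha on the same outcome. The consequence ranges from nothing (50-point rule only), through mild conservatism (one-sided 0.05 total, O'Brien-Fleming-type), to an overall error of 0.028–0.037 against 0.025, or about 0.053 against 0.05. All the non-zero figures assume that non-inferiority is testable at each look, that looks are equally spaced, and that the spending function is one the plan does not name. The point matters for a borderline result and is worth settling in advance because the repair is cheap.

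**What to change.** Before any interim data are seen, adopt one of the following.

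**(a) No early declaration of non-inferiority.** State in the Stopping Criteria that interim analyses test only for a difference between arms and that non-inferiority is assessed once, at the end. Keep the 95% interval in the Analysis Plan. Remove the interim allowance from the sample size paragraph, and restate the calculation for a fixed one-sided 0.025 design: about 180 per group for 80% power, or about 78% power at 172 per group. Removing the allowance without this restatement would leave 172 without a derivation. If 172 is kept, the cost is wording and a slightly lower stated power.

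**(b) Non-inferiority tested at the looks.** Name the spending function and an overall one-sided 0.025 in the Stopping Criteria. Set the final interval in the Analysis Plan to the remaining level: about 95.6–95.8% for O'Brien-Fleming-type spending with equally spaced looks, recomputed from the actual information fractions. The 95% interval can still be reported descriptively. The cost is about 1 point of power (78.2% to about 77% at 172 per group), and the stated 80% should be amended to match.

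In both cases, reconcile the Lan-DeMets boundary with the 50-point threshold, so that it is clear which governs an interim decision and for which hypothesis.

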## **METHODS**

Timeline: After randomization and distribution of study materials participants will have study visits every 3 months for 12 months to ascertain colonization status and development of subsequent SSTI.

Inclusion criteria: Households which participated in the "Community-Associated Methicillin-Resistant Staphylococcus aureus (CA-MRSA) Among Household Members and the Home Environment" study (HRPO 201104330). Only participants providing written, informed consent, or for whom consent is provided by a parent or legal guardian, will be included.

Exclusion Criteria: Households in which all members experienced SSTI during the 12-month natural history study will be ineligible to participate in the trial, to eliminate the bias that would be introduced if these families were randomized to the Individualized Approach arm. We will also not approach individuals who have declined contact for future studies on the HRPO 201104330 study consent form.

Procedures: The households participating in the "Community-Associated Methicillin-Resistant Staphylococcus aureus (CA-MRSA) Among Household Members and the Home Environment" (HRPO 201104330) study will be invited to enroll in this randomized trial upon completion of the 12-month follow-up period.

Randomization: Due to logistics and the use of objective outcome measures, this study will be performed as an open trial. Enrolled households will be allocated to one of two treatment groups (household vs. individualized decolonization) 1:1 randomization using the minimization method to assure balance in family size and composition (e.g., number of household members experiencing SSTI in the prior year). Minimization is a dynamic randomization algorithm that will help to ensure that treatment arms are balanced with respect to our predefined household factors as well as the number of households in each group. REDCap will be used to implement the minimization algorithm. Assignments will be generated by the REDCap program and revealed to the study coordinator immediately prior to the enrollment visit

Enrollment visit: Will take place in the participants' homes

- Time: 30-45 minutes
- The PI or research coordinator will provide standardized hygiene education curriculum regarding handling of lotions, soaps, hygiene items, and linens.
- Participants will be given instructions on how to perform the decolonization regimen (described below).

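### The upper limit that decides non-inferiority comes from only 1,000 household bootstrap samples, with no stated seed or interval type, so a borderline verdict can turn on the random seed

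*Combined protocol and SAP*

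**What the plan says.** The analysis plan for the primary outcome (Statistical Plan, Analysis Plan) reduces the trial to one comparison: "Non-inferiority will be defined as the upper limit of the 2-sided 95% confidence interval being less than 10% (our margin of non-inferiority". On how the interval is obtained, it says: "One thousand sample bootstrapping (household sampling with replacement) will be used to estimate the 95% confidence interval and account for clustering within households".

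The documents do not say whether the interval is percentile, BCa, bootstrap-t or normal-based. They give no seed, do not say whether households are resampled separately within each arm, and have no rule for a limit that lands close to 10%. A later paragraph of the Analysis Plan promises that critical results will be checked against GEE models, but gives that check no part in the non-inferiority decision.

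The sample-size paragraph supplies the design figures: "The expected rate of SSTI in individuals in the Household Approach group is 9% at 3 months based on one of our prior studies", an inflation factor of 1.4 for clustering, and "a total sample of 344 participants (172 per group) or 86 total households (43 households per group) will have 80% power at alpha=0.05". After attrition it expects more than that minimum: "we will have 90 households for analysis of the primary outcome SSTI at 3 months".

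**The concern.** A bootstrap limit carries two kinds of error. One is sampling error, which only more households can reduce. The other is Monte Carlo error, which depends only on the number of resamples and can be made negligible by computing longer. If the 97.5th percentile of 1,000 resamples is used, 0.025 × 1,000 = 25 values lie beyond it, so the limit moves visibly from one run to the next.

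For a descriptive interval that would hardly matter. Here the limit is compared with a fixed threshold to give a pass or a fail, and a borderline result could pass under one seed and fail under another. No feature of the data would explain the difference.

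**Working it through.** **Inputs.** From the sample-size paragraph: 9% in the Household Approach arm, margin 10 points, inflation 1.4, 172 participants and 43 households per arm, and 90 households expected at analysis (45 per arm under 1:1 allocation). From the Analysis Plan: B = 1,000.

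Assumed, because the documents do not say: equal households of 344/86 = 4; beta-binomial clustering with intraclass correlation (1.4 − 1)/(4 − 1) = 0.133; resampling within arm.

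**1. The plan's own figure.** The standard error of the difference at 9% in both arms is √(2 × 0.09 × 0.91 × 1.4/172) = 0.0365, or 3.65 points. The decision rule is one-sided at 0.025, and fixed-design power is Φ(0.10/0.0365 − 1.96) = 78.2%, close to the stated 80%. The stated 172 per group lies between 129 × 1.4 = 180.6 (one-sided 0.025, no interim looks) and 168.5 to 170.1 (one-sided 0.05, Pocock-type spending, four or five looks). The 3.65 points is therefore a fair basis for what follows.

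**2. Monte Carlo SD of the upper limit.**

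- Percentile limit: √(0.975 × 0.025/B)/φ(1.96) × SE. With B = 1,000 this is 0.00494/0.0584 × 3.65 = 0.31 points (95% range about ±0.6). With B = 10,000 it is 0.10.
- Normal-based limit: 1.96 × SE/√(2B). With B = 1,000 this is 1.96 × 3.65/44.7 = 0.16 points. With B = 10,000 it is 0.05.

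**3. Chance that two seeds disagree, by formula (percentile).** This is the density of the upper limit at 10% times the mean absolute difference between two Monte Carlo draws. At no true difference the limit is centred at 1.96 × 3.65 = 7.15 points. Its density at 10 is φ((10 − 7.15)/3.65)/3.65 = 0.081 per point, and the mean absolute difference is (2/√π) × 0.31 = 0.35 points. The product is 2.8%. The same calculation gives 3.8% at a true difference of 3 points and 3.2% at 5 points. With B = 10,000 the three values are 0.9%, 1.2% and 1.0%.

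**4. The same by simulation.** 40,000 trials per scenario, 43 households of four per arm, percentile limit:

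| True rates | Seed SD, B = 1,000 (points) | Seeds disagree, B = 1,000 | Seeds disagree, B = 10,000 |
|---|---|---|---|
| 9% vs 9% | 0.35 | 2.5% | 0.8% |
| 12% vs 9% | 0.37 | 3.6% | 1.0% |
| 14% vs 9% | 0.38 | 2.8% | 0.9% |
| 19% vs 9% | 0.41 | 0.6% | 0.2% |

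The simulated SD with B = 10,000 is 0.18 to 0.20 points. Simulated SDs exceed the formula partly because, with 172 per arm, possible differences move in steps of 1/172 = 0.58 points. Taking 1.96 × 0.31 = 0.6 and 1.96 × 0.41 = 0.8, a verdict is exposed when the limit is within roughly 0.6 to 0.8 points of 10%.

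**5. Width, if the limit is a percentile limit.** With 43 households per arm its half-width relative to a t-based one (84 degrees of freedom) is about √(42/43) × 1.96/1.989 = 0.974. The upper limit is then low by 3.65 × (1.989 − 1.96 × √(42/43)) = 0.19 points at 9% vs 9%, and by 0.23 points at 9% vs 19%. The implied one-sided error is 2.8% against a nominal 2.5%.

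Simulated false non-inferiority at 9% vs 19%, over the runs made:

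- 43 households of four per arm: percentile 3.2% to 3.7%, t limit 2.5% to 2.9%.
- 45 households of four per arm: percentile 2.7% to 2.8%, t limit 2.7% to 2.9%.
- Households of two to six, 43 or 45 per arm: percentile 2.8% to 3.2%, t limit 2.3% to 2.8%.

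Part of the contrast between 43 and 45 is the grid. With 180 per arm a 10-point difference is exactly 18 participants, and a limit equal to 10% fails the rule. With 172 it would be 17.2, which is not an attainable value.

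**The case against.** The strongest reply is that the effect is small. Seed noise of 0.3 to 0.4 points sits beside a sampling error of 3.65 points, and most trials would give the same verdict under any seed. That stands, and it is why the point is minor. It does not justify keeping the noise, since removing most of it costs nothing.

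A second reply is that the GEE validation already gives a seed-free, cluster-aware check. It may do so, but it may be meant only for the regression models described in that paragraph. It has no stated bearing on the verdict, so it would not settle a borderline case.

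A reader might go further and infer that the primary interval is anti-conservative. The documents do not support that. They never say the limit is a percentile limit, and at the 45 households per arm that the plan expects, with four members each, the percentile and t limits had practically the same simulated error. A reader might also conclude that the bootstrap should give way to a t limit. Household resampling is a legitimate way to handle clustering. In the 40,000-trial simulation at 9% vs 9%, the t limit lowered the chance of declaring non-inferiority from 80.0% to 77.5%, and making it decisive would make the number of resamples irrelevant to the verdict. That trade-off is debatable and does not correct an error.

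Finally, the missing seed does not show that one would be chosen after seeing the data. It only leaves that question open.

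**Conclusion.** The concern holds as a minor, freely avoidable weakness. With 1,000 samples and a percentile limit, the deciding figure has a Monte Carlo SD of about 0.3 to 0.4 points. Two seeds disagree in about 2.5% to 3.6% of trials at true differences of 0 to 5 points, against about 1% with 10,000 samples. A normal-based limit would carry about half that noise. The size rests on equal households of four, beta-binomial clustering at 0.133, and resampling within arm; none of these is stated in the plan.

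The possible narrowness is a secondary, conditional remark: about 0.2 points if the limit is a percentile one, with a simulated one-sided error of about 2.7% to 3.7% depending on the number and size of households.

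**What to change.** In the primary-outcome paragraph of the Analysis Plan, replace the 1,000 samples with: *at least 10,000 bootstrap samples, drawn by household within arm, with a pre-specified seed*. In the same sentence, name the interval type. Both changes are needed: a fixed seed makes the result repeatable but no more accurate, and 10,000 samples still leave about 1% disagreement between seeds.

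Optionally, report a household-level cluster-robust limit, using the t distribution on (households − 2) degrees of freedom, beside the bootstrap limit as a sensitivity check. The bootstrap limit should remain the basis of the decision.

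The cost is a sentence of text and seconds of computing. Nothing changes in participants, data collection or the margin, and power is not reduced by drawing more samples.
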